8.0 Intervention Conditions

8.1. Starting the Conversation. The STC intervention consists of a 25-minute video accessible via smartphone, computer or tablet, and an accompanying 5-page workbook providing information and targeted skills training for communicating with providers about sexual concerns. In addition, women will receive a 2-page resource guide consisting of information about institutional and external resources on sexual and menopausal health related to gynecologic cancer and its treatment.³⁰ The video includes a slideshow with narration and will be made available through a link sent to participants via email; the workbook in paper format and will be sent via mail. All participants will be sent the resource guide several weeks prior to an upcoming scheduled clinic visit with instructions to read it prior to their visit. Women in the STC intervention arm will also be sent a link via email to the video with instructions to watch the video and complete the exercises in the accompanying workbook prior to their upcoming visit. Participants in both conditions will receive a reminder call close to their scheduled visit, and those who have not reviewed materials close to their visit will be offered the opportunity to come early to their visit and view the materials using a study tablet immediately prior to their clinic encounter in a private space.

STC intervention content was initially developed based on formative qualitative work with breast cancer patients and clinicians on knowledge and skills gaps and intervention preferences⁸⁴ and by principles of social cognitive theory,⁵⁹ which emphasize building self-efficacy through learning skills for effectively discussing sexual health concerns. Menopausal issues were also included because the treatments commonly given to women with hormonal-dependent breast cancer eliminate estrogen (e.g., aromatase inhibitors, chemotherapy, ovarian suppression) and therefore cause both distressing sexual and menopausal symptoms.¹⁰⁴⁻¹⁰⁷ To maintain consistency with the initially tested intervention while enhancing relevance for gynecologic cancer, we include menopausal issues but focus on genito-urinary symptoms of menopause (e.g., vaginal symptoms, urinary symptoms), since they tend to be highly associated with women's sexual function difficulties.^{4,39}

8.2. Control. Women in the control condition will receive the Resource Guide³⁰ only. The guide will be sent via email to facilitate easy use of webpages by clicking directly on listed links.

9.0 Risks to Participants

This is a behavioral study with few risks. The major risks for study subjects are: (1) discomfort at answering study questions on surveys, or during discussions with clinicians that occur during the trial, although women are free to choose how and what they say during their visit with their clinician to participate and are not required to change anything about their communication, and (2) loss of privacy or confidentiality. Due to the protections we will have in place, we believe these risks to be minimal. Patients will be informed that they do not have to answer any survey items that cause distress or discomfort, and that they are not required to discuss any topics related to sexual health with their clinicians if they do not wish.

10.0 Potential Benefits to Participants

We hope that participants will receive some benefit through participating in the study. However, they may receive no benefit. Patients in both the STC condition or the control condition will receive a handout with reputable resources and evidence-based information about effects of gynecologic cancer on sexual and menopausal health, and they may find this information useful in addressing concerns or in

suggesting resources (e.g., websites) that they could turn to for further information. Patients assigned to the STC intervention may gain skills related to clinical communication about sexual health, which may have a beneficial effect on patient-provider interactions or on aspects of their health, including their sexual health or function, but this cannot be guaranteed. Findings from this study may inform future research on patient-provider communication and sexuality in gynecologic cancer as well as guide the development of interventions to improve the quality of care for patients with gynecologic cancer and potentially other types of cancer or medical conditions. The minimal risks to subjects are reasonable in relation to potential benefit in improving the care of patients with gynecologic cancer.

11.0 Provisions to Maintain the Confidentiality of Data

In order to minimize the risks associated with discomfort in answering questions, participants will be told that they do not have to answer any research questions and that, if they change their mind about participating, they can stop at any time. In order to minimize the risks associated with loss of confidentiality, all patient data will be kept confidential and secure and will be de-identified for analytic purposes. All computers with patient or provider data will be password protected with access restricted to study investigators, and all paper data forms will be kept in locked cabinets. Each participant will have an identifying number that links to his/her name. Access to the linkage list will be limited to study team members and kept in a secure file. A second log will be used to track the number of patients invited to participate, the number who agreed, and the number who refused. This second log will have no personal identifying information, only the patient study number (for patients), the decision on whether to participate, and the reason for refusal, if any. We are concerned with ensuring that our questions about sexuality are handled in a sensitive manner and will assure patients that participation in the research study will not affect their clinical care. In the case that a patient shows increased psychological distress such that continuation in the study is contraindicated, the patient's participation will be terminated and the patient will be given resources including contact information for appropriate mental health professionals.

12.0 Costs to Participants

There are no costs to participants in this study. Self-report data will be obtained at an already scheduled clinic encounter of the patient and parking is free, so there are no costs associated with extra visits or parking.

13.0 Off-Study Criteria

Any participant may leave the study at any time due to distress or other reasons. We do not have a priori reasons for letting participants off the study.

14.0 Drugs and Devices

Not applicable.

15.0 Multi-Site Research Study

Not applicable.

16.0 Statistical Analysis

16.1. Statistical Analyses for Aim 1

16.1.1. Primary and Secondary Outcome Variables

16.1.1.1. Primary outcomes are feasibility and acceptability of the study. Feasibility will be measured through study enrollment, retention (defined as completion of the final survey), and intervention completion (defined as engaging in some or all of the intervention components (i.e., video and workbook; STC arm only)). We will also assess completion of the resource guide across both study conditions, although these data will not be used to determine feasibility. Acceptability is measured using standard self-report items obtained at post-intervention (immediately following clinic encounter); specifically, these items assess intervention satisfaction, informativeness, helpfulness, relevance, ease of participation, liking the format, likelihood of recommending to others, and perceived importance of the program for people with gynecologic cancer.

16.1.2.1. Feasibility. The proportion of study subjects meeting each feasibility measure will be calculated. The following rates will be used as benchmarks for feasibility: Enrollment \geq 60% of eligible candidates; retention \geq 80%; and intervention completion \geq 70%. For enrollment, we will approach patients until clinical communication data are collected on 30 participants, and then stop approaching patients. If we meet our target of 30 enrollments by approaching 50 or fewer patients, the intervention will be declared as feasible.

16.1.2.2. Acceptability. At the individual level, we will determine whether the individual met our acceptability criteria, which we define as endorsing 75% of the 8 acceptability items for the core components of the STC intervention (video and workbook; at least 6 out of 8 items). If 75% of the STC sample (n=15) meets that definition, then we will be able to say that overall the study meets the standard set for acceptability. Other data obtained from the acceptability surveys (e.g., length of time spent using intervention materials, qualitative survey responses) will be analyzed descriptively or using thematic analysis as appropriate. These items will be analyzed across both conditions.

16.1.2.3. Preliminary efficacy. Prior to analyzing outcome data, we examine internal reliability of the outcome measures. In line with recommendations for the analysis of data from pilot studies¹⁰⁸ preliminary outcome data will only be analyzed descriptively, and no formal hypothesis testing will be conducted. Instead we will calculate means and mean differences (from baseline to follow-up assessments) with their respective standard deviations and 95% confidence intervals. Standard effect sizes will also be calculated. These results will inform power calculations for a larger, definitive study.

Analyses for Exploratory Aims. The exploratory aim will characterize the feasibility, acceptability, and preliminary effects of the STC intervention by women's partnered status and level of sexual concerns. We will generate standard descriptive statistics within strata defined by partnered status (partnered vs. not partnered) and level of sexual concerns obtained on the HRQOL scale at baseline. Frequencies, proportions, means, medians, and standard deviations will be calculated and presented. In addition, we will conduct exploratory hypothesis-generating analyses on the novel measure of body compassion, which is assessed only at baseline. For the body compassion data (obtained at baseline only), similar descriptive statistics will first be conducted, as well as exploratory correlational analyses between the body compassion scale and study outcomes, and socio-demographic/clinical correlates or Chi-square for categorical factors.

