2.0 Objectives

The central goal of this study is to examine the feasibility, acceptability, and preliminary efficacy of the newly adapted STC intervention on patient-clinician communication about sexual health. However, there are additional issues that are understudied and could be informative to the design of a larger trial that we intend to examine through three exploratory aims. First, although we know that sexual health discussions be held for gynecologic cancer patients who are partnered and unpartnered, there is little information known about how women's partnered status might influence the appropriateness or efficacy of the STC intervention. Thus, in an exploratory aim, we will examine whether women's partnered status is associated with the feasibility, acceptability or preliminary effects of the STC intervention with any of the study outcomes. As level of sexual concerns may also play a role, we will examine that along with partnered status. We expect that the information we collect on partner participation and the preferences regarding this will be informative for our larger trial.

Specific Aim 1. To assess the feasibility and acceptability of the STC intervention in a pilot study in women with gynecologic cancer.

Hypothesis 1. STC will be judged as feasible, determined through measures of rates of participant enrollment, retention, and intervention completion.

Hypothesis 2. STC will be judged as acceptable, determined through post-intervention evaluations of intervention satisfaction, informativeness, relevance, helpfulness, ease of participation, approval of the format, likelihood of recommending to others, and perceived importance of the program for people with gynecologic cancer.

Specific Aim 2. To assess the preliminary effects of the STC intervention on patient-clinician communication about sexual health and on patients' sexual and psychological health outcomes.

Hypothesis 3. STC will show positive effects on patients' self-efficacy for clinical communication about sexual health concerns from baseline to post-intervention and 2-month follow-up, and their clinical communication about sexual health concerns (discussing sexual health concerns; raising the topic; asking a question about sexual health) at their post-intervention clinic encounter.

Hypothesis 4. STC will show positive effects on patients' sexual function, activity, and psychological distress from baseline to 2-month follow-up.

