4.0 Study Design

4.1 Overall Study Design

In this pilot study, 30-36 women with a diagnosis of any stage gynecologic cancer will be randomized 2:1 to either the Starting the Conversation (STC) condition, a multimedia intervention aimed at enhancing sexual health communication consisting of a skill-building video and workbook with a resource guide, or

to a control condition offering the resource guide only. We may randomize up to 36 patients in the event that some participants are unable to provide communication data (e.g., due to attrition or cancellation of clinic visits), with the goal of collecting clinic communication data on 30 women. The objective of this study is assess feasibility, acceptability, and preliminary effects of the STC intervention, in an effort to guide the design of a larger planned randomized controlled trial to determine intervention efficacy. Feasibility will be measured through rates of study enrollment, retention, and intervention completion. Acceptability will be assessed through post-intervention evaluations of intervention satisfaction, informativeness, relevance, helpfulness, ease of participation, approval of the format, likelihood of recommending to others, and perceived importance of the program for people with gynecologic cancer. Preliminary efficacy will be assessed through estimating the intervention effect size, if appropriate, or through looking descriptively at means and confidence intervals on improved. In Aim 2, validated self-report measures will assess intervention-related change in patients' self-efficacy for sexual health communication and sexual and psychological health outcomes from baseline to 2-

Table 1. Recruitment Totals				month follow-up. Data for exploratory aims will be assessed using patients' self-report data at baseline (for socio-demographic factors), their medical chart review (for clinical factors), or at post-intervention (for their thoughts and preferences on partner participation).
Number of subjects per year projected at FCCC	Total number of subjects at FCCC	Number of subjects nationally or internationally (if applicable)	Number of subjects at collaborating institutions (if applicable)	
Up to: 42	Up to: 42	N/A	N/A	

report data at baseline (for socio-demographic factors), their medical chart review (for clinical factors), or at post-intervention (for their thoughts and preferences on partner participation).

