6.0 Measures and Self-Report Data Collection

6.1. Clinician Measures. Clinician self-report data include socio-demographic and clinical self-report items (e.g., length of time in practice, clinical role) and are collected at the time of consent.

6.2. Patient Measures. Patients will complete self-report surveys immediately after enrolling (baseline; T1), at an in-person clinic encounter with their gynecologic cancer clinician several weeks after receiving the intervention materials (post-intervention; T2), and at 2-month follow-up (T3). Self-report data collection will generally be completed using REDCap, a secure, HIPAA-compliant web-based application used successfully in multiple trials in our lab, with paper-and-pencil versions available for those who lack computer access. T2 surveys, which are completed in-clinic immediately following the clinic encounter, will be paper-and-pencil. For patients who are unable to stay in-person to complete their paper survey, online versions of the form will be sent via email to the patient for completion using a link to the online survey with instructions for the patient to complete the survey as soon as possible. Medical data will be gathered through chart review by a qualified member of the research team.

Aim 1. Aim 1 measures include those pertaining to the feasibility and acceptability of the STC intervention in women with gynecologic cancer.

Feasibility will be measured through measures of participant enrollment, defined as the percent of eligible candidates approached who enroll, retention to study completion, defined as completion of all study surveys, and rates of intervention completion, defined by self-report responses on the program evaluation.

Acceptability of the STC intervention will be measured through self-report program evaluation survey administered at post-intervention (after clinic encounter). The main items considered outcomes for this aim are: intervention satisfaction, informativeness, helpfulness, relevance, ease of participation, approval of the format, likelihood of recommending to others, and perceived importance of the program for people with gynecologic cancer. Other items in the program evaluation will assess other aspects of the intervention and may include open-ended items to gather further information that could be useful in improving the intervention content for the larger trial.

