16.1.2 Sample Size

This study will enroll a total of 30-36 patients, of which 20-24 will be assigned to the intervention and 10-12 assigned to control. The objective of this study is to pilot test the newly adapted STC intervention for women with gynecologic cancer and to allow us to calculate effect sizes, if appropriate, that will inform a larger R01 trial that is expected to follow from this study. We selected 30 participants to participate in this trial because it is a large enough sample to provide ample pilot data while maintaining adequate feasibility in the time allotted. The target sample size is similar to those used in successful prior pilot trials used by the study team.¹⁰⁹ Further, we have chosen a 2:1 allocation to the STC condition, which allows us to gather greater information from participants in this condition, our primary interest, relative to the control condition. The operating characteristics of the feasibility and acceptability rules for this pilot study are given in Table 4. Although we may over-recruit to ensure adequate communication data, feasibility and acceptability rules (see Table 4) will be conducted using the first 30 participants. Probabilities were calculated using the negative binomial distribution for enrollment, and using the binomial distribution for all other feasibility and acceptability benchmarks.

Table 4: Operating characteristics of feasibility and acceptability decision rules

Criteria	Decision rule	Favorable condition	Unfavorable condition	Probability of declaring success if favorable	Probability of declaring success if unfavorable
Enrollment	≥ 60% enrolled (30 accrued with ≤50 approached)	75%	45%	99%	2%
Retention	≥ 80% enrolled (≥ 24/30 enrolled)	90%	65%	97%	6%
Completion	≥70% complete (≥14/20 on STC arm)	80%	50%	91%	6%
Acceptability	≥75% endorse at least 6/8 items (≥15/20 on STC arm)	85%	55%	93%	6%

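### The only thresholded rule that declares STC feasible uses enrollment alone, although feasibility is defined by three criteria and no rule combines them

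*Combined protocol and SAP*

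**What the plan says.** Three places define feasibility by the same three measures.

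- Section 2.0, Hypothesis 1: "STC will be judged as feasible, determined through measures of rates of participant enrollment, retention, and intervention completion".
- Section 4.1: "Feasibility will be measured through rates of study enrollment, retention, and intervention completion".
- Section 16.1.1.1, which names feasibility as a primary outcome: "Feasibility will be measured through study enrollment, retention (defined as completion of the final survey), and intervention completion".

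Section 16.1.2.1 states "The proportion of study subjects meeting each feasibility measure will be calculated". It then introduces three thresholds with "The following rates will be used as benchmarks for feasibility": 60% for enrollment, 80% for retention and 70% for intervention completion. After a sentence about when approaches to patients will stop, it closes with the verdict: "If we meet our target of 30 enrollments by approaching 50 or fewer patients, the intervention will be declared as feasible".

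Table 4 in section 16.1.2 (Sample Size) gives each criterion its own decision rule and its own probability of success. It has no row for an overall feasibility verdict. The text above it says that "feasibility and acceptability rules (see Table 4) will be conducted using the first 30 participants".

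On retention, section 6.2 (Aim 1) has "retention to study completion, defined as completion of all study surveys", whereas section 16.1.1.1, quoted above, requires only the final survey.

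**The concern.** The verdict sentence and the definition do not match. The definition has three parts; the sentence that turns data into a declaration uses one. Enrollment is also the measure that says least about the intervention, because a woman enrolls before she receives any material. Poor retention or low use of the video and workbook is what a pilot of this kind should detect, and under the sentence as written neither would prevent a feasible verdict.

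If the sentence was meant to settle only the enrollment criterion, the plan has no overall verdict rule. The team would then have to choose one after seeing the three results. Acceptability, in the next paragraph, does have an individual rule, a sample rule and an overall verdict, so the gap is specific to feasibility.

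The two retention definitions add a second ambiguity. A woman who completes the final survey but not the post-intervention (T2) survey counts as retained under one and not under the other. Section 6.2 foresees women who cannot stay to complete T2 in clinic and are sent it online, so such cases are possible.

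**Working it through.** **Inputs (Table 4, section 16.1.2).** Enrollment: 30 accrued from at most 50 approached, favorable 75%, unfavorable 45%. Retention: at least 24/30, 90% and 65%. Completion: at least 14/20 in the STC arm, 80% and 50%. Acceptability: at least 15/20 in the STC arm, 85% and 55%.

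**Step 1: reproduce Table 4.** Enrollment is the negative binomial probability that the 30th enrollment falls within 50 approaches, which equals P(Bin(50, p) ≥ 30). The others are binomial tails.

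| Criterion | Formula | Favorable (stated) | Unfavorable (stated) |
|---|---|---|---|
| Enrollment | P(Bin(50, p) ≥ 30) | 0.9937 (99%) | 0.0235 (2%) |
| Retention | P(Bin(30, p) ≥ 24) | 0.9742 (97%) | 0.0586 (6%) |
| Completion | P(Bin(20, p) ≥ 14) | 0.9133 (91%) | 0.0577 (6%) |
| Acceptability | P(Bin(20, p) ≥ 15) | 0.9327 (93%) | 0.0553 (6%) |

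All eight entries reproduce. They are one-criterion probabilities and do not describe an overall verdict.

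**Step 2: compare the sentence as written with a rule requiring all three.** Products assume that the criteria are independent, which the documents do not state. Without that assumption, the joint probability is at most the smallest of the three and at least their sum minus 2 (or zero).

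| True rates | Sentence as written | All three, independent |
|---|---|---|
| Enrollment favorable; retention and completion unfavorable | 0.9937 | 0.9937 × 0.0586 × 0.0577 = 0.0034 |
| Only retention unfavorable | 0.9937 | 0.9937 × 0.0586 × 0.9133 = 0.0532 |
| Only completion unfavorable | 0.9937 | 0.9937 × 0.9742 × 0.0577 = 0.0558 |
| All favorable | 0.9937 | 0.9937 × 0.9742 × 0.9133 = 0.8841 |

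Bounds under any dependence:

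- First row: 0 to min(0.9937, 0.0586, 0.0577) = 0.0577.
- Last row: 0.9937 + 0.9742 + 0.9133 − 2 = 0.8812, up to 0.9133.
- Last row with acceptability added: 0.8841 × 0.9327 = 0.8246, with bounds 0.8139 (the four probabilities summed, minus 3) and 0.9133.

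**Step 3: the retention definition.** The baseline survey is completed before randomization (section 7.0), so among randomized women the definitions differ only through T2. Suppose that Table 4's 90% is final-survey completion and that 5% to 10% of those women lack T2. Both are assumptions; the documents give neither.

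- 5% lacking T2: 0.90 × 0.95 = 0.855, and P(Bin(30, 0.855) ≥ 24) = 0.866.
- 10% lacking T2: 0.90 × 0.90 = 0.81, and P(Bin(30, 0.81) ≥ 24) = 0.660.

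The stated 97% would then be 66% to 87% under the all-surveys definition.

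**The case against.** The strongest reply is that the sentence concerns enrollment only. The one before it opens with an enrollment lead-in, its content is the enrollment row of Table 4, and separate rules for retention and completion would be pointless if enrollment decided alone. On that view, naming the intervention is a slip. This is probably what the authors intended. It does not rescue the text: the sentence declares the intervention feasible, and if it covers enrollment alone, no section states how the overall verdict is reached. Hypothesis 1 ties the verdict to all three measures but gives neither thresholds nor a combination rule.

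A second reply is that 99% against 0.3% is a corner case. The earlier breast cancer trial (section 3.0, Preliminary Data) reported 97% retention and material use above 85%. At 97% and 85%, P(at least 24/30) exceeds 99.9% and P(at least 14/20) is 97.8%, so the two rules would differ by only about 2 percentage points. That is fair as a forecast, although it comes from another population. A decision rule should still be judged at the unfavorable values that the plan itself chose for Table 4.

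Third, each component rate will be calculated, so a reader could see any conflict, and nothing in the documents makes the larger trial conditional on the label. Both points stand and limit the harm.

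Fourth, the retention range rests on assumptions. If Table 4's 90% already meant all surveys, 97% stands. If the first 30 participants are the 30 with clinic communication data, which is collected at T2, the two definitions coincide. This limits the numerical claim but not the conflict in wording.

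Finally, requiring all three is one possible rule. It is the one that follows most directly from the three-part definition; any other would also have to be written down before analysis.

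**Conclusion.** The concern holds, and the text should be corrected. As written, the one rule that yields a feasible verdict on this primary outcome ignores two of its three defining criteria, and no combination rule exists elsewhere. At Table 4's own unfavorable values for retention and completion, with enrollment favorable, the probability of a feasible verdict is 99%. It would be 0.3% if all three were required (independence), or at most 5.8% under any dependence. If only retention or only completion is unfavorable, it would be 5.3% or 5.6% (independence).

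Confidence is high that the combination rule is missing and that the two retention definitions conflict. How much the retention wording matters is uncertain, because the 66% to 87% range depends on an assumed share of missing T2 surveys. Table 4's existing entries need no change.

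**What to change.** In section 16.1.2.1, replace the verdict sentence with:

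> The enrollment criterion is met if the 30th enrollment occurs by the 50th eligible patient approached. STC is declared feasible only if the enrollment, retention and intervention completion criteria in Table 4 are all met.

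This leaves the restriction to the first 30 participants in section 16.1.2 as it is.

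Use one retention definition throughout. Keeping the final survey is simplest, because that is the definition in the statistical section that sets the 80% benchmark; section 6.2 should be aligned with it.

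Optionally, add a line under Table 4 with the joint probabilities when all rates are favorable: about 88% for the three feasibility criteria assuming independence (88% to 91% without it), and about 82% with acceptability included (81% to 91%).

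The cost is two sentences in 16.1.2.1, one definition in 6.2 and the optional line. No new data, procedures or sample size are needed. The stricter rule lowers the chance of a feasible verdict under favorable rates from 99% to about 88%, which the team should accept knowingly.

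### Does the 93% chance of passing on acceptability in Table 4 conflict with the 80% completion rate in the row above it?

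*Combined protocol and SAP*

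**What the plan says.** Acceptability is one of the primary outcomes in Section 16.1.1.1. Under Section 16.1.2.2 a patient meets the criterion by endorsing at least 6 of 8 items about the video and workbook, and the study passes as follows: "If 75% of the STC sample (n=15) meets that definition, then we will be able to say that overall the study meets the standard". Table 4 in Section 16.1.2 repeats the rule as "≥75% endorse at least 6/8 items (≥15/20 on STC arm"), with a favourable rate of 85% (93% chance of success) and an unfavourable rate of 55% (6%).

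The completion row reads "≥70% complete (≥14/20 on STC arm"), with 80% favourable (91%) and 50% unfavourable (6%). Section 16.1.1.1 gives completion a loose meaning, "defined as engaging in some or all of the intervention components", so a non-completer used neither the video nor the workbook.

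Both measures come from one form. Section 6.2 describes "rates of intervention completion, defined by self-report responses on the program evaluation", and also says: "Acceptability of the STC intervention will be measured through self-report program evaluation survey administered at post-intervention". Both rules apply to the same people, since "feasibility and acceptability rules (see Table 4) will be conducted using the first 30 participants"; at 2:1 allocation that means 20 in the STC arm. The probabilities were obtained "using the binomial distribution for all other feasibility and acceptability benchmarks", one row at a time.

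The plan does not say how an STC patient who used neither component, or who returned no program evaluation, counts towards the 15.

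**The concern.** The acceptability items ask about materials that a non-completer has not seen. The natural scoring is that such a patient does not endorse them, and then the endorsing share of the arm cannot be larger than the using share. Table 4 nevertheless puts 85% endorsement beside 80% use in the same 20 patients and calls both favourable. Read together, the two rows cannot both hold, and the 93% appears to overstate the chance of passing a primary benchmark.

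There is also a scoring question. At 80% use about 4 of the 20 patients (20 × 0.20) would be non-users. With a cut-off of 15, two analysts who treated those four differently could reach opposite verdicts. The results are meant to guide a larger trial, so it would matter if the rule were open or its stated performance wrong.

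**Working it through.** **Inputs.** From Table 4: n = 20; completion cut-off 14, rates 80% and 50%; acceptability cut-off 15, rates 85% and 55%. From Section 3.0, Preliminary Data: use of the video and workbook in the earlier breast cancer trial was above 85%. Assumption not in the plan: non-users count as not endorsing.

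**1. Reproduce Table 4.** With X ~ Bin(20, p):

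- Completion: P(X ≥ 14) = 0.913 at p = 0.80 and 0.058 at p = 0.50 (stated 91% and 6%).
- Acceptability: P(X ≥ 15) = 0.933 at p = 0.85 and 0.055 at p = 0.55 (stated 93% and 6%).

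All four figures are right for their own inputs.

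**2. Impose the assumption.** Let u be the share of the arm that uses the materials and q the share of users who endorse at least 6 of 8 items. The endorsing share of the arm is p = u × q, which is at most u. For p = 0.85 at u = 0.80, q would have to be 0.85/0.80 = 1.06, which is impossible. The best case is q = 1.

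| Use u | Users endorsing q | p = u × q | P(X ≥ 15) |
|---|---|---|---|
| 0.80 | 1.00 | 0.80 | 0.804 |
| 0.80 | 0.95 | 0.76 | 0.657 |
| 0.85 | 1.00 | 0.85 | 0.933 |
| 0.85 | 0.95 | 0.8075 | 0.828 |
| 0.90 | 0.95 | 0.855 | 0.941 |

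So the 93% requires use of at least 85%. At exactly 85% use every user must endorse; at 90% use, 0.85/0.90 = 94.4% of users must.

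**3. A pass on completion with acceptability out of reach.** At 80% use, exactly 14 users occurs with probability 0.913 − 0.804 = 0.109. Completion then passes and 15 endorsers cannot be found. This follows from setting the benchmarks at 70% and 75%; it is not a computing fault.

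**4. Apply the same logic to the unfavourable column.** Table 4 puts 55% endorsement beside 50% use. If the rows were joint, this pair would also be impossible, and the ceiling on wrongly passing acceptability would be P(X ≥ 15) at p = 0.50, which is 0.021 rather than 6%. Raising favourable use to 85% (completion row 0.978) or restating 93% as at most 80% would leave this pair untouched. Neither edit would make the table jointly consistent.

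**5. Other scoring choices.** If non-users may endorse, 85% is restored at 80% use when every user and (0.85 − 0.80)/0.20 = 25% of non-users endorse. If only users are counted, with the cut-off at 75% of users, 80% use and 85% or 55% of users endorsing, the probabilities of passing are 0.879 and 0.062. That is a different rule from the one written.

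**The case for a change.** The strongest case for a change is that this is a pass/fail rule on a primary outcome and the plan leaves one of its inputs unwritten. Non-use is expected: the favourable completion rate itself allows for 20% of the arm, and Section 8.1 provides for patients who have not reviewed the materials near their visit. A reader of Table 4 is not told that 93% presumes at least 85% use. A sentence or two would settle it before any data are seen.

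Part of this stands. The scoring convention is missing, and the 93% should not be read as the chance of passing at 80% use.

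The claim that the table is wrong does not stand. Each favourable rate is set 10 to 15 points above its own benchmark (75 against 60, 90 against 80, 80 against 70, 85 against 75), which is how separate design points are chosen. A favourable point for one rule is not a ceiling for another. The plan's own evidence also suggests use above 80%: the earlier trial exceeded 85%, completion here needs only some engagement, and Section 8.1 adds reminder calls and viewing on site before the visit.

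The room for rival scoring is narrow as well. The denominator is written as 20 STC patients, not users or respondents. A patient with no evaluation has not endorsed six items and does not count towards 15. The only open case is a patient who used nothing yet returns a form endorsing six or more items about the video and workbook.

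**Conclusion.** No change is needed. Table 4 lists marginal operating characteristics, each correct for its stated input; none of its figures needs correcting. The apparent shortfall, 80.4% against 93%, holds only if true use is 80% and non-users are scored as not endorsing. It disappears at 85% use with full endorsement among users (93.3%) or at 90% use with 95% endorsement (94.1%). If use were as low as 50%, the same scoring would put the chance of wrongly passing at no more than 2.1%, below the stated 6%.

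What remains is a gap that an analyst fills sensibly from the rule as written: count the STC patients among the first 30 who endorsed at least 6 of 8 items, divide by 20, and treat everyone else as not meeting the criterion. Reporting endorsement among users beside that figure would help readers separate low use from poor acceptability, but this is optional. The sample size is unaffected, because Section 16.1.2 bases the 30 participants on having enough pilot data, on what is practicable in the time, and on earlier pilots of similar size, not on these probabilities.
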